## 5.6 End of Treatment Visit (7 [+3] Days after the Last Dose of ARQ 087)

If possible, the End of Treatment Visit should be performed 7 [+3] days after the last dose of ARQ 087. The following assessments will be made during the End of Treatment Visit:

- Physical examination, including mucous membranes and skin
- ECOG PS
- Vital signs (weight, temperature, blood pressure, respiration rate, and pulse)
- Fasting clinical blood tests (see Section 6.4)
- Urinalysis (see Section 6.4)
- Serum pregnancy test, if applicable (see Section 6.4)
- 12-lead ECG (see Section 6.3)
- Echocardiography or MUGA scan to measure LVEF, if applicable (see Section 6.3)
- Blood samples for tumor marker(s), if applicable (to be tested at study site)
- Blood samples for pharmacokinetics (except Expanded Cohort, see Section 6.5)
- Tumor measurement and staging if not done within four weeks (28 days) prior to the end of treatment visit (see Section 6.7)
- AEs assessment
- Record concomitant medications

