## 5.8 Discontinuation from the Treatment/Study

Subjects will be removed from the study treatment at any time if they meet any of the following criteria:

- Documented radiographic or clinical progression of disease\*
- Noncompliance with any part of the study, as evaluated by the Investigator and Medical Monitor
- Clinically unacceptable toxicities despite optimal treatment or dose reduction
- Withdrawal of consent
- Investigator's decision (in agreement with the Sponsor/Medical Monitor or designee)
- Lost to Follow-up
- Death

\* Subjects may remain on treatment if, in the opinion of the Investigator and with the agreement of ArQule's Medical Monitor, they continue to derive benefit from the treatment.

Subjects will be removed from the study if they meet any of the following criteria:

- Safety follow-up visit is completed per protocol and drug-related AEs have resolved to baseline, CTCAE Grade 1, stabilized, or are deemed irreversible.
- Withdrawal of consent
- Lost to Follow-up
- Death

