#### Evaluation of Best Overall Response

The best overall response is the best response recorded from the start of the study treatment until the end of treatment. No confirmatory measurement for CR or PR is required in this study.

The subject’s best overall response assignment will depend on the findings of both target and non-target disease and will also take into consideration the appearance of new lesions.

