### Best Overall Response: All Time Points

The best overall response is determined once all the data for the subject is known.

*Best response determination in trials where confirmation of complete or partial response IS NOT required:* Best response in these trials is defined as the best response across all time points (for example, a subject who has SD at first assessment, PR at second assessment, and PD on last assessment has a best overall response of PR). When SD is believed to be the best response, it must also meet the protocol specified minimum time from baseline of 8 weeks. If the minimum time is not met when SD is otherwise the best time point response, the subject's best response depends on the subsequent assessments. For example, a subject who has SD at the first assessment, PD at second the assessment, and does not meet the minimum duration for SD, the subject will have a best response of PD. The same subject lost to follow-up after the first SD assessment would be considered inevaluable.

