### Frequency of Tumor Re-evaluation

In this study, tumor measurement will be conducted at Baseline, and then in 8-week intervals while the subject is on treatment or as clinically indicated until progression of disease,

withdrawal of consent, death, or loss to follow-up. Tumor measurement will also be performed during the End-of-Treatment visit if it is not done within 28 days of the visit date.

Baseline tumor assessments must be performed within four weeks (28 days) of the first dose of treatment.

All efforts should be made to ensure consistency between the baseline measurements and all subsequent measurements in reference to utilization of scanning methods, equipment, technique (including slice thickness and field of view), and the radiographic interpreter.

The radiological evaluation must include CT or MRI scanning of the chest, abdomen, and pelvis. Any additional suspected sites of disease should also be imaged. All evaluations should meet the standard of care for imaging of lesions in the respective organ(s).

All target and non-target sites are evaluated at each time point of tumor assessment.

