3.2.4 Efficacy Variables

Best Overall Response (BOR)

The best overall response is determined once all the data for the subject is known. No confirmatory measurement for CR or PR is required in this study. The best overall response is defined as the best response (in the order of CR, PR, SD, and PD) among all overall responses recorded from the start of treatment until the last radiographic tumor assessment (for example, a subject who has SD at first assessment, PR at second assessment, and PD on last assessment has a best overall response of PR). When SD is believed to be the best response, it must also meet the protocol specified minimum time from baseline, 8 weeks (± 3). If the minimum time is not met when SD is otherwise the best time point response, the subject's best response depends on the subsequent assessments. For example, a subject who has SD at first assessment, PD at second and not meeting minimum duration of SD will have a best response of PD. The same subject lost to follow-up after the first assessment would be considered non-evaluable.

Objective Response Rate (ORR)

For purposes of determining the objective response rate (ORR), tumor response will be based on the best overall response recorded for each subject from the date of first dose. The ORR will be calculated as the number of subjects with a complete or partial response divided by the total number of subjects [ORR= (CR+PR)/# subjects].

Disease Control Rate (DCR)

Disease Control Rate (DCR) is defined as the proportion of subjects with the best overall responses of CR, PR and SD [DCR= (CR+PR+SD)/# subjects].

Duration of Objective Response

Duration of objective response is defined as the time from the date of the measurement criteria are first met for CR/PR (whichever is first recorded) until the first date that recurrent or progressive disease is documented.

If a subject is discontinued, dies, or is lost to follow-up with no documentation of progressive disease, duration of response is defined as the time from the date of the first documentation of objective response to the date of the last tumor assessment as a censored value. Duration of response will be measured for responding subjects (PR or CR) only.

Duration of Stable Disease

Duration of stable disease is defined as the time from the start of the treatment until the criteria for disease progression are met.

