If a subject is discontinued or dies, or is lost to follow-up with no documentation of progressive disease, duration of stable disease is defined as the time from the date of first dose to the date of the last tumor assessment as a censored value. Duration of stable disease is measured for any subject who has best overall response of SD.

Progression-Free Survival (PFS)

Progression Free Survival (PFS) is defined as time from first dose until documented radiographic disease progression or death, whichever occurs first.

If a subject is discontinued from study due to reasons other than radiographic disease progression or death, PFS is censored as the time from the date of first dose to the date of the last tumor assessment. Only assessments with CR, PR SD or NE as overall tumor response are treated as last tumor assessment.

If a subject has no baseline tumor assessment and/or has no post baseline tumor assessment, this subject is to be censored at the date of first dose for PFS.

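### Best overall response has no cut-off at first documented progression, so a subject treated past PD can count in DCR or ORR while already being a PFS event

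*SAP*

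**What the plan says.** SAP 3.2.4 orders the categories CR, PR, SD, PD and takes the best "among all overall responses recorded from the start of treatment until the last radiographic tumor assessment". Protocol Appendix 6 describes the window twice. The paragraph headed Evaluation of Best Overall Response puts it this way: "The best overall response is the best response recorded from the start of the study treatment until the end of treatment". Under Best Overall Response: All Time Points: "Best response in these trials is defined as the best response across all time points". None of the three names first progression as an end point. A single scan is enough for a response, since SAP 3.2.4 states: "No confirmatory measurement for CR or PR is required in this study".

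PFS in the same SAP section does stop at progression: "Progression Free Survival (PFS) is defined as time from first dose until documented radiographic disease progression or death, whichever occurs first".

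Protocol 5.8 makes documented radiographic or clinical progression a reason to stop treatment, then adds an exception. It begins "Subjects may remain on treatment if, in the opinion of the Investigator" and also requires the Medical Monitor's agreement that benefit continues.

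On scanning, Protocol 5.5.1 and 6.7 schedule a tumor assessment every eight weeks, with no exemption for a subject who has progressed. The End of Treatment list in 5.6 includes "Tumor measurement and staging if not done within four weeks (28 days) prior to the end of treatment visit". Appendix 6, Frequency of Tumor Re-evaluation, is worded differently: scans are at eight-week intervals "while the subject is on treatment or as clinically indicated until progression of disease", followed by withdrawal of consent, death or loss to follow-up.

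**The concern.** Progression is normally the end of the period in which a subject can earn a best response. Without that limit, the rule can turn a PD into an SD or a PR and never the reverse, so any error in ORR and DCR is upward. Only subjects kept on drug after progression can be affected, and they are selected by judgement that they are still benefiting.

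Protocol 10.2.3 names response rate, disease control rate and PFS as the evidence of activity. Under the present rule two of the three can contradict the third for the same person. BOR may also drive the iCCA futility look in SAP section 7, and the logistic regression of CR, PR and SD against PD in SAP 5.4.3.

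**Working it through.** The documents give no figure to reproduce on this point, so the check applies their own rules to example subjects.

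**Inputs.** From Appendix 6, Evaluation of Target Lesions: PD is a rise of at least 20% and at least 5 mm over the smallest sum on study, and PR is a fall of at least 30% from the baseline sum. From SAP 3.2.4: SD needs about 8 weeks from baseline, and no confirmation is needed. The sums below are illustrative and assume no new lesion and no non-target PD.

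**Subject A: 100 mm at baseline, 122 mm at week 8, 115 mm at week 16.**
- Week 8: (122 − 100)/100 = +22%, and +22 mm, so PD.
- Week 16: the smallest sum is still 100 mm; (115 − 100)/100 = +15%, below 20%, so SD.
- BOR by the SAP: best of {PD, SD} = SD. Week 16 exceeds the 8-week minimum, so the subject counts in DCR.
- BOR cut at first PD: PD.
- PFS: event at week 8.

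**Subject B: as A, but the later sum is 70 mm or less.**
- (70 − 100)/100 = −30%, so PR.
- BOR by the SAP: PR, counted in ORR and DCR. BOR cut at first PD: PD. PFS: event at week 8.

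**Subject C: 100, 125, 130 mm.** PD at both scans, and BOR is PD under either rule. Being treated past progression is not enough by itself; the sum must fall back.

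**Durations (SAP 3.2.4).**
- Subject A: duration of SD runs from treatment start until progression criteria are met, which is week 8. The scan that earned the SD is at week 16.
- Subject B, with the PR at week 16: duration of response runs from that PR to the first date on which progression is documented. Read literally, that is 8 − 16 = −8 weeks.

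Both definitions presuppose that response comes before progression. The BOR window does not ensure it.

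**Weight of one subject (100/n).** n=10: 10.0 points. n=50: 2.0. n=60: 1.7. The first is the iCCA interim; the others are the planned range of the Expanded Cohort.

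**iCCA interim (assuming responses are counted by the SAP 3.2.4 definition).** SAP section 7 continues at 30% or more, that is 3 of 10. One PR after PD turns 2/10 (20%, exact 95% CI 2.5 to 55.6%) into 3/10 (30%, 6.7 to 65.2%), and stop becomes continue. Protocol section 10 instead stops at 30% or less. Under that wording the critical step is from 3/10 to 4/10 (40%, 12.2 to 73.8%).

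**The case against.** The strongest reply is the Appendix 6 sentence on scan frequency. On one natural reading scheduled scans end at progression, so the last radiographic assessment would normally be the PD scan and the problem would not arise. That reading is available, but it does not settle the matter. The sentence governs when to scan, not which scans enter BOR, and Protocol 5.5.1, 5.6 and 6.7 carry no such stop. What it does show is that the documents are not consistent about scanning after progression.

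It can also be said that the case is uncommon. Stopping at progression is the default, continuation needs two parties to agree, and under the Appendix 6 time-point table a new lesion or non-target PD keeps the assessment at PD whatever the target sum does. This stands, and it limits the frequency. Equivocal progression is handled separately in Appendix 6 and is not the case at issue.

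The response and target-lesion listings in SAP 5.4.5 would let a reader find such subjects. That is true, but the tabulated rates would still include them.

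The worked examples in SAP 3.2.4 might be thought to imply a stop at PD. They cover SD, PR, PD and SD followed by an early PD. Neither covers PD followed by something better.

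Finally, the primary objective is safety, no hypothesis is tested (SAP 5.1), and the Protocol synopsis calls anti-tumor activity exploratory. This stands and lowers the severity.

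**Conclusion.** The gap is real: as written, BOR can improve after first documented PD, and it then contradicts PFS and the duration endpoints for the same subject. The effect is upward only. Its size is 10 points per subject at n=10 and 1.7 points per subject at n=60. One post-PD PR changes the iCCA interim decision only if the count is next to the threshold. The point rests on three conditions: a subject continues after PD under 5.8, a later scan is done, and the sum falls back with no persisting new lesion or non-target PD. It should be fixed before database lock, but it does not threaten the primary objective.

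Three stronger readings are tempting and not supported:
- **An overall bias in percentage points.** This would need the share of subjects treated past PD and the share of those with a later non-PD scan. The documents give neither.
- **Responses to later therapy inflating ORR.** The SAP window indeed has no stop at new anticancer therapy, and the Protocol's end-of-treatment limit is not repeated there. However, Protocol 7.7.2 bars concurrent anticancer therapy (apart from limited palliative radiotherapy), and no scan is scheduled after the End of Treatment visit, 7 (+3) days after the last dose. The practical effect is small.
- **A distorted response table for 30 iCCA subjects (10 plus up to 20).** SAP 5.2 and 5.4.5 tabulate efficacy by dose group and overall, and specify no such table.

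**What to change.** - **SAP 3.2.4.** Restrict BOR to assessments from first dose up to and including the first documented radiographic PD, dated as for PFS. For completeness, also require that they precede any new anticancer therapy.
- **Protocol Appendix 6.** Give both BOR paragraphs the same window.
- **Scanning after progression.** Reconcile the Appendix 6 frequency sentence with Protocol 5.5.1, 5.6, 5.8 and 6.7, so that it is clear what is expected for a subject who continues under the exception.
- **Reporting.** List assessments made after first PD separately, outside ORR and DCR.

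The cost is one sentence in the SAP, matching edits in Appendix 6 and one listing. The assessments and progression dates needed are already collected. ORR and DCR may come out slightly lower.

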#### Duration of Overall Response

The duration of overall response is measured from the time measurement criteria are first met for CR/PR (whichever is first recorded) until the first date that recurrent or progressive disease is objectively documented (taking as reference for progressive disease the smallest measurements recorded on study).

The duration of overall complete response is measured from the time measurement criteria® that are first met for CR until the first date that recurrent disease is objectively documented.

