5.4.5 Efficacy Analyses

Efficacy analysis will be performed based on both safety and evaluable populations.

Objective Response Rate and Disease Control Rate

The best overall tumor response (CR, PR, SD, PD and not evaluable), objective response rate and disease control rate will be tabulated by treatment group and overall on the safety population and evaluable population. The percent of subjects in each treatment group will be provided along with the 95% confidence interval of the percentage. In addition, the related listings will also be presented.

Percent change from the minimum sum of longest diameters (including baseline, if that is the minimum value, up to the preceding tumor assessment) and the percent change from baseline for the sum of longest diameters will be computed in the listings for target lesions. A waterfall plot will also be utilized to display the relationship between minimum sum of longest diameters change and current cancer types.

Progression Free Survival

Progression free survival will be estimated based on Kaplan-Meier estimate (product limit) for both safety and evaluable population. The median PFS and the 95% confidence interval will be estimated, and the corresponding Kaplan-Meier plots will be also presented.

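### The SAP censors deaths without documented progression for duration of response and of stable disease but counts them as PFS events; this biases duration upward by an unknown, possibly zero, amount.

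*SAP*

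**What the plan says.** SAP 3.2.4 starts duration of objective response when CR or PR criteria are first met and runs it "until the first date that recurrent or progressive disease is documented". The next paragraph covers subjects without that documentation: "If a subject is discontinued, dies, or is lost to follow-up with no documentation of progressive disease, duration of response is defined" by counting from first documented response "to the date of the last tumor assessment as a censored value". Death is thus handled like discontinuation or loss to follow-up. The variable is restricted to responders: "Duration of response will be measured for responding subjects (PR or CR) only".

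Duration of stable disease starts at the beginning of treatment and has the parallel rule: "If a subject is discontinued or dies, or is lost to follow-up with no documentation of progressive disease, duration of stable disease is defined" likewise, with censoring at the last tumor assessment.

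PFS, in the same section, is different: "Progression Free Survival (PFS) is defined as time from first dose until documented radiographic disease progression or death, whichever occurs first".

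Protocol Appendix 6 (Duration of Overall Response) ends response duration at progression, "until the first date that recurrent or progressive disease is objectively documented". Its paragraph on duration of stable disease ends at the progression criteria. Neither mentions death or gives a censoring rule.

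On analysis, SAP 5.4.5 states: "The best overall tumor response (CR, PR, SD, PD and not evaluable), objective response rate and disease control rate will be tabulated by treatment group". It adds listings, target-lesion changes, a waterfall plot and Kaplan-Meier PFS. It names no estimator or interval for either duration. Protocol 10.2.3 and 10.3.4 likewise cover only response rate, disease control rate and PFS.

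**The concern.** Censoring tells the Kaplan-Meier method that the subject remained at risk and, after that date, behaves like those still being followed. That does not fit a responder who has died. Such a patient may well have been progressing unseen, so the censoring is informative. Even if the deaths were unrelated to the tumor, the result would describe how long responses would last if nobody died, which is not how a reader takes a reported duration of response.

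The protocol leaves room for such deaths. Treatment may stop for clinical progression (5.8), and Appendix 6 does not count symptomatic deterioration as objective progression. Scans are eight weeks apart and may go to every three months after 11 cycles (6.7), so the longest-treated subjects can have the widest unobserved gaps.

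At stake is how the durability of responses is described. CR and PR need no confirmation, so a single scan can make a response. Because 5.4.5 gives no method, the choice of summary would also be open after the data are seen.

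**Working it through.** **No plan figure to reproduce.** The documents give no expected median duration, number of responders, event count or death share. The check compares the rules and then illustrates the size.

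**Step 1: the three definitions in SAP 3.2.4.**

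| Variable | Clock starts | Ends at | Death without documented progression |
|---|---|---|---|
| PFS | First dose | Radiographic progression or death | Event at date of death |
| Duration of response | First CR or PR | Progression or recurrence | Censored at last tumor assessment |
| Duration of stable disease | Start of treatment | Progression | Censored at last tumor assessment |

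For a subject with best response SD, the first and third rows share a starting point, so the treatment of death is the material difference between them.

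**Step 2: one hypothetical responder.** First PR at week 8, still PR at the week 24 scan, last dose at week 26, death at week 28. An end-of-treatment visit at week 27 would need no scan, because one was done within 28 days (Protocol 5.6). The death falls inside the 30-day follow-up (Protocol 5.7). PFS: event at 28 weeks. Duration of response: 24 - 8 = 16 weeks, censored.

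**Step 3: size under constant hazards.** Let h be the total hazard of progression or death during response, and p the share of first events that are deaths without documented progression.

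- Death as an event: median = ln 2 / h.
- Death censored: only the progression hazard h(1-p) is estimated, so median = ln 2 / [h(1-p)].
- Ratio = 1/(1-p).

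| Assumed p | 1/(1-p) | Overstatement of median |
|---|---|---|
| 0% | 1.000 | 0% |
| 5% | 1.053 | 5% |
| 10% | 1.111 | 11% |
| 20% | 1.250 | 25% |
| 30% | 1.429 | 43% |

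**Step 4: with eight-week scans.** A simulation of 20,000 responders took an assumed true median of 24 weeks to progression or death, with progression seen only at scans. Estimated proportion still in response at 24 weeks:

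| Assumed p | SAP rule | Death as event |
|---|---|---|
| 5% | 0.516 | 0.499 |
| 10% | 0.533 | 0.497 |
| 20% | 0.570 | 0.496 |
| 30% | 0.618 | 0.502 |

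The SAP-rule medians can only fall on scan dates (32 weeks for p of 5% to 20%, 40 weeks for 30%), so the 24-week proportion is the better comparison. The direction concerns the expected estimate. In a very small sample, moving the censoring date back to the last scan shrinks the risk set early and can briefly lower an individual curve.

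**Step 5: scale.** SAP section 7 allows 10 plus up to 20 iCCA subjects. At the 30% threshold used there, 0.30 × 30 = 9 responders. If all nine had an event and one was such a death, p = 1/9 and the factor is 1/(8/9) = 1.125.

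**The case against.** The strongest reply is that the progression-only endpoint is the protocol's own. Appendix 6 ends both durations at progression, and the SAP carries that over. This stands: a reader might infer that the SAP departs from the protocol, and on the endpoint it does not. What the SAP adds is the instruction to censor deaths, on which Appendix 6 is silent.

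A reader might also infer that PFS and duration of response contradict each other. They do not. They are two explicitly defined quantities, and one death can be an event for one and censored for the other. The objection is to the choice, which the SAP does not explain.

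Third, the size rests on assumption, and the affected median is one the SAP does not plan to report. This also stands. Such deaths may be few on record: scans are regular, an end-of-treatment scan is required unless one was done within 28 days, Appendix 6 asks for efforts to document progression after treatment stops, and required follow-up is at least 30 days, with no survival follow-up planned.

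Fourth, the stakes are limited. Anti-tumor activity is a secondary, descriptive objective; the iCCA enrollment rule uses response rate alone; and Kaplan-Meier PFS already counts these deaths. All true, and reason to keep the point modest. None of it justifies treating death as non-informative.

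**Conclusion.** The point holds in limited form. The SAP's rule biases duration of response and of stable disease upward whenever subjects die without documented progression. The illustrative overstatement of the median is 5% to 43% for p of 5% to 30%, assuming constant hazards; it is zero if no such death occurs. The documents supply no p, so none of these figures is a forecast.

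Two stronger readings should be resisted. One is that reported durations will be overstated by a particular percentage: that needs both a known p and a planned median, and the plan has neither. The other is that durability will go unreported: SAP 5.4.5 promises related listings, and the lists of tables and listings in SAP section 11 are empty in the text available, so a duration table cannot be ruled out. What can be shown is that 5.4.5 specifies no method for two variables that 3.2.4 defines. Alone, that would be mostly missing detail; it matters here because the only stated rule is the censoring rule. No hypothesis test, error rate or sample size is affected.

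**What to change.** In SAP 3.2.4, end duration of response, and duration of stable disease, at the earlier of documented progression (or recurrence) and death from any cause, as for PFS. Censor subjects with neither at the last evaluable scan. The PFS rule also accepts a not-evaluable assessment as the last one, so settle the censoring date once for all three variables. Record the difference from Protocol Appendix 6 in SAP section 9, which now reads N/A.

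If the sponsor prefers the progression-only measure, label it time to progression among responders and also report the version with death as an event.

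In SAP 5.4.5, report for responders the Kaplan-Meier median duration of response with 95% confidence interval and the number of events, split into progressions and deaths. The split lets a reader see p directly.

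The cost is a few sentences and one extra table, using dates already needed for PFS. The downsides are somewhat shorter durations if such deaths occur, and wide intervals with few responders.

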#### 10.2.3 Efficacy

Response rate/disease control rate and progression free survival will be used to determine preliminary evidence of activity.

Progression Free Survival (PFS) is defined as time from first dose until documented radiographic disease progression or death, whichever occurs first.

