### Missing Assessments and Inevaluable Designation

When no imaging/measurement is done at all at a particular time point, the subject is not evaluable (NE) at that time point. If only a subset of lesion measurements are made at an assessment, usually the case is also considered NE at that time point, unless a convincing argument can be made that the contribution of the individual missing lesion(s) would not change the assigned time point response. This would be most likely to happen in the case of PD. For example, if a subject had a baseline sum of 50 mm with three measured lesions and at follow-up only two lesions were assessed, but those gave a sum of 80 mm, the subject will have achieved PD status, regardless of the contribution of the missing lesion.

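### SAP 3.2.4 lets a not-evaluable (NE) assessment set the PFS censoring date, which can only raise the Kaplan-Meier curve or leave it unchanged

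*SAP*

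**What the plan says.** The protocol (10.2.3) defines the endpoint: "Progression Free Survival (PFS) is defined as time from first dose until documented radiographic disease progression or death, whichever occurs first". Neither that section nor 10.3.4.1 gives a censoring rule. The rule is in SAP 3.2.4. For a subject who leaves the study for a reason other than radiographic progression or death, "PFS is censored as the time from the date of first dose to the date of the last tumor assessment". The next sentence says which assessments qualify: "Only assessments with CR, PR SD or NE as overall tumor response are treated as last tumor assessment". If there is no baseline or no post-baseline assessment, "this subject is to be censored at the date of first dose for PFS".

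Protocol Appendix 6 gives NE two meanings. The first is a missed scan: "When no imaging/measurement is done at all at a particular time point, the subject is not evaluable (NE) at that time point". The second is an incomplete one: "If only a subset of lesion measurements are made at an assessment, usually the case is also considered NE at that time point". On frequency, Appendix 6 states that "tumor measurement will be conducted at Baseline, and then in 8-week intervals while the subject is on treatment". Protocol 6.7 allows 3-monthly scans after 11 cycles.

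On estimation, SAP 5.4.5 says: "Progression free survival will be estimated based on Kaplan-Meier estimate (product limit) for both safety and evaluable population". It adds the median, its 95% confidence interval and a plot. No sensitivity analysis of PFS censoring is planned.

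**The concern.** A PFS censoring date should be the last date on which the subject was known to be progression-free. An NE result does not show that. Consider a subject with SD at week 8 and NE at week 16 who then leaves the study. That subject is censored at week 16, although the last evaluable evidence is from week 8. If the only post-baseline result is NE at week 8, the subject appears to be credited with 8 weeks rather than censored at first dose, because the SAP lists NE as a qualifying assessment. Each NE visit at the end of follow-up adds one scan interval.

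PFS is one of the measures the protocol names for preliminary evidence of activity (10.2.3). The groups are small and there is no control arm, so a few such subjects can move the reported curve and median, and only upward. The risk is greatest if incomplete scans are commoner in subjects who are progressing. That is plausible, but the documents do not address it.

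**Working it through.** The plan has no PFS event count, expected median or power figure to reproduce. The check covers direction, two small examples and a simulation.

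**Inputs from the documents.** Censoring rule: SAP 3.2.4. Meaning of NE: Protocol Appendix 6. Scans every 8 weeks: Protocol 6.7. Visit window of 3 days either way: Protocol 5.5.1. Kaplan-Meier estimator: SAP 5.4.5.

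**Assumed, because the documents give no figure.** Exponential PFS with true median 16 or 24 weeks. A 5% or 10% chance at each visit that the result is NE and the subject then leaves. NE either independent of progression or twice as likely at a visit where progression would have been found.

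**Step 1: direction.** S(t) is the product of (1 − d/r) over event times up to t, where d is the number of events and r the number at risk. Moving a censoring time later can raise r and leaves d unchanged. No factor falls, so neither the curve nor the median can fall.

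**Step 2: two examples with 10 subjects.**
- Four PD at week 8; two with SD at week 8 then NE at week 16; two PD at week 16; two PD at week 24. SAP rule: S(16) = (1 − 4/10) × (1 − 2/6) = 0.60 × 0.667 = 0.40. Last evaluable scan: (1 − 4/10) × (1 − 2/4) = 0.60 × 0.50 = 0.30. The median is 16 weeks under both.
- Two with NE at week 8 as the only post-baseline result; four PD at week 8; two at week 16; two at week 24. SAP rule: S(8) = 1 − 4/10 = 0.60 and S(16) = 0.60 × (1 − 2/4) = 0.30, so the median is 16 weeks. Censored at first dose: S(8) = 1 − 4/8 = 0.50. The median is then 8 weeks if taken as the first time the curve reaches 50%, or (8 + 16)/2 = 12 weeks if the midpoint of the flat stretch is used.

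**Step 3: simulation.** There were 400,000 subjects per scenario, with scan dates spread uniformly over the window. PFS was read just after the week-24 window. Differences in points from complete scanning are in brackets, taken before rounding.

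| True median (weeks) | NE per visit | NE at progression | Subjects ending on NE | Complete scanning | SAP rule | Last CR/PR/SD |
|---|---|---|---|---|---|---|
| 16 | 5% | same | 15% | 0.353 | 0.363 (+1.0) | 0.344 (−0.9) |
| 16 | 10% | same | 28% | 0.353 | 0.374 (+2.1) | 0.335 (−1.8) |
| 24 | 5% | same | 20% | 0.501 | 0.511 (+0.9) | 0.493 (−0.9) |
| 24 | 10% | same | 35% | 0.501 | 0.520 (+1.9) | 0.484 (−1.7) |
| 16 | 5% | doubled | 20% | 0.354 | 0.384 (+3.0) | 0.359 (+0.5) |
| 16 | 10% | doubled | 36% | 0.354 | 0.418 (+6.4) | 0.367 (+1.3) |
| 24 | 5% | doubled | 24% | 0.500 | 0.527 (+2.7) | 0.506 (+0.6) |
| 24 | 10% | doubled | 42% | 0.501 | 0.559 (+5.8) | 0.516 (+1.5) |

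At 2% per visit, independent of progression, 6-9% of subjects end on NE and the SAP rule is high by about 0.4 points.

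**The case against.** **NE does not mean that nothing was looked at.** A reader might infer that the added time was never assessed for progression. The documents do not support that for a partial scan. In the Appendix 6 time-point table, NE arises when target lesions are not all evaluated, non-target disease has not progressed and there are no new lesions. Progression seen in the lesions that were measured is still scored PD. The accurate statement is that status was not fully established. An NE followed by a later evaluable scan, PD or death does not set the censoring date at all.

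**A missed scan may leave no date to censor at.** SAP 6.1.1 requires complete tumor assessment dates and treats them as derived from measurement dates. A subject with no post-baseline assessment is already censored at first dose. On that reading the rule bites mainly on partial scans. This narrows the point but does not remove it, because the SAP names NE without distinguishing the two kinds.

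**The size is easily overstated, and last-evaluable censoring is not free of bias.** If every scan falls exactly on weeks 8, 16 and 24, independent NE at 5%, 10% and 20% per visit gives about 2, 4 and 8-10 points of overstatement, and last-evaluable censoring looks unbiased. Both results come from tied dates, where an NE subject counts as at risk for every progression found at that visit. With the protocol's window, the overstatement roughly halves, and last-evaluable censoring runs low by about as much as the SAP rule runs high. The per-visit rates are also large: 20% means about 46-55% of subjects end on NE.

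**Little depends on PFS.** The primary objective is safety, no hypothesis is tested (SAP 5.1), and the interim decision uses objective response (SAP 7). This stands, and it limits the point to a minor one.

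**Conclusion.** The point holds as a minor one. The SAP allows the end of progression-free follow-up to be dated at a visit where progression status was not fully established, and nothing else in the plan corrects this. The direction follows from the estimator and needs no assumption.

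The size does need assumptions. Under those listed, 24-week PFS is overstated by about 1-2 points when NE is independent of progression (about 15-35% of subjects ending on NE). It is overstated by about 3-6 points when NE is twice as likely at progression (about 20-42%). If few subjects end on NE, the effect is negligible.

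Censoring at the last evaluable scan is about 1-2 points low in the independent case and about 0.5-1.5 points high in the other. With independent NE it is therefore no more accurate than the SAP rule. Its advantage lies in the case that matters most, where deteriorating subjects have incomplete scans. Only the descriptive curve, median and confidence interval are affected. No test, error rate or enrollment decision is.

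**What to change.** In SAP 3.2.4:
- Remove NE from the list of responses that qualify as the last tumor assessment, so that PFS is censored at the last assessment with overall response CR, PR or SD.
- State that a subject with only NE results after baseline, and no PD or death, is censored at first dose.
- Use the same definition for duration of response and duration of stable disease. Both are censored at the last tumor assessment, and neither defines it.
- Keep the current rule as a sensitivity analysis, and report how many subjects end on NE so that readers can judge the difference.

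The cost is a few words and minor programming, with no change to data collection. Some censoring times become shorter, and PFS may look slightly less favourable.
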